7.5.1 Additional Guidance for Withdrawal Criteria

Any signs of suicidal risk will be assessed throughout the study by C-SSRS and MADRS assessments and clinical judgment of the investigator. If the subject has a significant risk of suicide in the opinion of the investigator, or the subject has the MADRS score of ≥ 5 on item 10 (suicidal thoughts), the subject will prematurely discontinue the study.

If subject's underlying diseases become exacerbated, and the investigator concludes any excluded medications or treatment is required, the subject will prematurely discontinue the study.

7.6 Procedures for Discontinuation or Withdrawal of a Subject

The investigator may discontinue a subject's study participation at any time during the study when the subject meets the study termination criteria described in Section [7.5](#). In addition, a subject may discontinue his or her participation without giving a reason at any time during the study. Should a subject's participation be discontinued, the primary criterion for termination must be recorded by the investigator. In addition, efforts should be made to perform all procedures scheduled for the Early Termination Visit.

8.0 CLINICAL TRIAL MATERIAL MANAGEMENT

This section contains information regarding all medication provided directly by the sponsor, and/or sourced by other means, that are required by the study protocol, including important sections describing the management of clinical trial material.

8.1 Study Medication

8.1.1 Dosage Form, Manufacturing, Packaging, and Labeling

In this protocol, the term study medication refers to all or any of the drugs defined below.

Table 8.a Study Medication

Name	Active Substance	Dosage Form	Strength	Manufacture
Lu AA21004 tablet	1-[2-(2,4-dimethyl-phenyl sulfanyl)-phenyl]-piperazine, hydrobromide	Indistinguishable round biconvex tablets	10 mg or 20 mg	Takeda Pharmaceutical Company Limited
Placebo tablet	None		—	

The study medications are identical in appearance.

As for the study medications for the placebo lead-in period, 14 tablets of placebo are packaged in 1 press-through pack (PTP) sheet, and a single sheet is enclosed in an outer carton. The 1 outer carton (including 7 days' spare tablets) will be provided to each subject in the placebo lead-in period.

As for the study medications for the double-blind treatment period, 14 tablets of Lu AA21004 or placebo are packaged in 1 PTP sheet. For Week 1 in the double-blind treatment period, 1 sheet (including 7 days' spare tablets) is enclosed in an Inner Carton 1, and, for Weeks 2 to 8 in the double-blind treatment period, 5 sheets (including 21 days' spare tablets) are enclosed in an Inner Carton 2. Inner Cartons 1 and 2 are packed together in an outer carton. The 1 outer carton will be provided to each subject in the double-blind treatment period.

The outer carton is labeled with a note that the formulation therein is used for a clinical study and pertinent information of the name and quantity of the study medication, the sponsor's name and address, manufacturing number, and storage conditions.

8.1.2 Storage

The study medications should be stored at room temperature (1°C to 30°C).

The study medication must be kept in an appropriate, limited-access, secure place until it is used or returned to the sponsor or designee for destruction. The study medication must be stored under the conditions specified on the label, and remain in the original container until dispensed. A daily temperature log of the drug storage area must be maintained every working day.

8.1.3 Dose and Regimen

For the placebo lead-in period, administration of the study medication will be started on the day after Visit 2, and subjects will orally take 1 tablet of placebo once daily.

For the double-blind treatment period, administration of the study medication will be started on the day after Visit 3, and subjects will orally take 1 tablet of Lu AA21004 at a dose of 10 mg or 20 mg or placebo once daily.

The investigator or designee should instruct subjects to take the study medication at the same time, a certain time in the morning to the extent possible, throughout the study. The study medication can be taken under both fed and fasted conditions.

At each visit, subjects will be provided with necessary and sufficient amount of the study medications to be used by next visit by the investigator or designee. The investigator or designee must instruct subjects to bring the all remaining study medication and container (PTP sheets) at each visit.

The dose (tablet count) that will be provided to each group and regimen are shown in [Table 8.b](#).

Table 8.b Dose and Regimen

Treatment Group	Regimen	Tablet Count/Dose		
		Placebo Lead-in Period	Double-blind Treatment Period (Week 1)	Double-blind Treatment Period (Weeks 2 to 8)
Placebo Group	Oral, once daily	Placebo tablet ×1	Placebo tablet ×1	Placebo tablet ×1
Lu AA21004 10 mg/day Group	Oral, once daily	Placebo tablet ×1	Lu AA21004 10 mg tablet ×1	Lu AA21004 10 mg tablet ×1
Lu AA21004 20 mg/day Group	Oral, once daily	Placebo tablet ×1	Lu AA21004 10 mg tablet ×1	Lu AA21004 20 mg tablet ×1

8.1.4 Overdose

An overdose is defined as a known deliberate or accidental administration of the study medication to or by a study subject, at a dose above that which is assigned to that individual subject according to the study protocol. This includes any concomitant medication received at a dose greater than that prescribed to the subject.

All cases of overdose will be documented as AEs on an AE page of the eCRF according to Section [10.2.1](#), and should be reported as a special interest AE according to Section [10.2.1.3](#) (with or without associated AEs). Serious adverse events (SAEs) associated with an overdose should be reported according to the procedure in Section [10.2.2](#).

In the event of an overdose of the study medication, the investigator should take general symptomatic and supportive treatment, along with immediate gastric lavage where appropriate. Intravenous fluids should be administered as needed. As in all cases of drug overdose,

respiration, pulse, blood pressure, and other appropriate signs should be monitored and general supportive treatment should be conducted.

8.2 Study Drug Assignment and Dispensing Procedures

Subjects will be assigned to receive the next available medication ID number allocated to each study site. The Medication ID Number will be entered onto the eCRF.

8.3 Randomization Code Creation and Storage

Randomization personnel (a person designated by the sponsor) will generate the randomization code. All randomization information will be stored in a secured area, accessible only by authorized personnel.

8.4 Study Drug Blind Maintenance

The emergency key code administration center will maintain the emergency key code until its breaking for an emergency or completion of database lock of all subjects.

Since analytical results of the plasma concentration may jeopardize maintenance of study blinding, the analytical laboratory will keep the final analytical results and not disclose to a third party until unblinding of the study. The analytical laboratory will report the results to the sponsor after they receive the notification of unblinding of the study. However, the analytical laboratory may disclose the results to the sponsor through a responsible person for randomization before unblinding of the study taking measures to secure the blinding such as reassignment of the medication number so that persons in the laboratory may not identify a subject. The detailed procedure will be specified in the separately created manual for handling of biological specimen for pharmacokinetic analysis.

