9.1.17 Pharmacokinetic Sample Collection and Analysis

9.1.17.1 Collection of Blood for Pharmacokinetic Sampling

Blood samples will be collected in concurrence with blood collection for clinical laboratory tests. The exact date and time of the blood collection and dosing times of the last 2 doses prior to the blood collection will be recorded on the eCRF. Refer to the separately created procedure for collection, handling, and shipping of blood samples.

Since drug concentrations of subjects in the placebo group will not be measured, the assignment personnel will send an operation manual to the central laboratory to identify samples of subjects in the placebo group. Drug concentration data will be reported to the sponsor after unblinding of the study.

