13.0 STATISTICAL METHODS

13.1 Statistical and Analytical Plans

A statistical analysis plan (SAP) will be prepared and finalized prior to unblinding of subject's treatment assignment. This document will provide further details regarding the definition of analysis variables and analysis methodology to address all study objectives.

A blinded data review will be conducted prior to unblinding of subject's treatment assignment. This review will assess the accuracy and completeness of the study database, subject evaluability, and appropriateness of the planned statistical methods.

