2.4 Statistical/Analytical Issues

2.4.1 Adjustments for Covariates

After blind data review, it was decided not to conduct further adjustments for covariates by adding variables.

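### Protocol 8.4 lets drug concentrations reach the sponsor before unblinding, 9.1.17.1 says only afterwards, and the one named safeguard is not aimed at the sponsor

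*Protocol*

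**What the plan says.** Protocol 8.4 (Study Drug Blind Maintenance) starts from the premise that concentration results could undermine the blind. Its default is that the laboratory keeps them and does "not disclose to a third party until unblinding of the study", reporting to the sponsor once it has been told of unblinding. It then makes an exception: "the analytical laboratory may disclose the results to the sponsor through a responsible person for randomization before unblinding of the study", provided steps are taken to protect the blind. The one step named, as an example, is "reassignment of the medication number so that persons in the laboratory may not identify a subject". Detail is left to a separate manual on handling PK specimens, which is not among the documents.

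Protocol 9.1.17.1 gives the timing with no exception: "Drug concentration data will be reported to the sponsor after unblinding of the study". The same section contains two facts that bear on how well renumbering works. First, the laboratory is told which samples are placebo: "Since drug concentrations of subjects in the placebo group will not be measured". Second, "The exact date and time of the blood collection and dosing times of the last 2 doses prior to the blood collection" go onto the eCRF.

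On what happens before unblinding, protocol 13.1 states: "A blinded data review will be conducted prior to unblinding of subject's treatment assignment". The SAP is also finalised in that period. Under 13.1.1 the data handling rules, which hold the exact analysis-set definitions, are fixed before database lock. SAP 2.4.1 records one decision of this kind: "After blind data review, it was decided not to conduct further adjustments for covariates by adding variables".

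**The concern.** Two current sections of the protocol give different answers to whether the sponsor may hold concentration data while the trial is still blinded. A release that 8.4 permits would breach 9.1.17.1. The issue is one that 8.4 itself identifies as a threat to the blind.

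The safeguard also points the wrong way. Renumbering is described as stopping people in the laboratory from identifying a subject, yet the party receiving the data is the sponsor. The sponsor holds the eCRF, runs the blinded review, judges evaluability and sets the data handling rules. If concentrations arrive in a form that can be linked to subjects before those steps are closed, it becomes hard to show that the decisions were made without knowledge of treatment. PK is only an additional objective (5.1.3), so early release does nothing for the primary comparison.

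**Working it through.** The plan states no figure on this point, so there is none to reproduce. The conflict is a matter of text. The arithmetic below only gauges what a linkable early transfer could reveal.

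**1. The sections side by side.** Release to the sponsor before unblinding:
- 8.4, default: no.
- 8.4, exception: yes, through the person responsible for randomization and with blinding measures.
- 9.1.17.1: no, with no exception and no cross-reference to 8.4.

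The same pair of provisions stands in all three protocol editions in the file, so this is not a by-product of an amendment.

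**2. What renumbering removes.** Protocol 8.2 puts the medication ID on the eCRF. Reassigning that number breaks the link through the ID. It does not touch draw date, draw time or dosing times, which are also on the eCRF.

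**3. Whether draw times could restore the link.** Suppose an early transfer did carry the draw date and time. Assume one draw per subject, 480 subjects, draws spread evenly over 365 to 730 calendar days on weekdays (5/7 of days) in 8-hour clinic days, and times recorded identically in both sources. The number of possible slots is K = days × 5/7 × slots per day, and P(a given time is unique) = (1 − 1/K)^479.

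| Resolution | Slots per day | 365 days | 730 days |
|---|---|---|---|
| Date only | 1 | 0.159 | 0.399 |
| 5 minutes | 96 | 0.981 | 0.990 |
| 1 minute | 480 | 0.996 | 0.998 |

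Draws clustered in the morning would lower these values. If times are withheld, these fields give no link.

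**4. What a link reveals about active versus placebo.** Placebo samples are not assayed, so a result linked to a subject means an active arm. Among subjects whose eCRF shows a PK draw, having no result points to placebo. At full enrolment the ceiling is 2 × 160 = 320 active and 160 placebo subjects. The true number is lower, because PK samples are listed only at Visits 6 and 8 (9.3.4, 9.3.5) and are not taken at early termination. A subject who stops before Visit 6 has no PK sample in any arm.

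**5. What a link reveals about 10 versus 20 mg.** Protocol 4.1.1 states linear PK from 2.5 to 60 mg, so mean concentrations differ about 2-fold. The documents give no between-subject CV, so a range is assumed. With log-normal concentrations and a cut at the geometric midpoint, P(correct) = Φ((ln 2 / 2)/σ), where σ = √ln(1 + CV²).

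| Assumed CV | Correct | Wrong |
|---|---|---|
| 30% | 0.88 | 0.12 |
| 40% | 0.82 | 0.18 |
| 50% | 0.77 | 0.23 |
| 60% | 0.73 | 0.27 |
| 70% | 0.71 | 0.29 |

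For CV 50%: σ = √ln 1.25 = 0.472; 0.347/0.472 = 0.73; Φ(0.73) = 0.77. Chance is 0.50, so one concentration makes the dose probable but not known.

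**The case against.** The strongest reply is that this is one rule written once with its exception and once without. Early disclosure under 8.4 is routed through the person responsible for randomization and is conditional on protecting the blind. Renumbering is only an example, and the procedure itself sits in a manual that may well mask draw and dosing times. Observed concentrations are kept out of the eCRF (12.1), so results and times start in separate places and could be merged after unblinding. All of this stands, and it limits the point.

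A reader might infer that early results would reveal every subject's arm in spite of renumbering. The documents do not support that. Nothing says that times travel with an early transfer. A renumbered result belongs to no identifiable subject until some link is made. A missing result does not prove placebo in a subject who was never sampled. Dose would be only probable, on an assumed CV.

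A reader might also infer that the primary result is biased. That is not shown either. Protocol 13.1.3 already fixes the MMRM terms, covariance structure, degrees of freedom and Holm thresholds, and 13.1.1 gives the FAS an objective definition. The SAP version 2 change table lists no change to section 2.1.1, and the covariate decision was to add nothing. The remaining discretion is mainly per-protocol membership and data evaluability. Nor do the documents show that any early release took place.

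The reply does not remove the conflict. A manual cannot settle which of two protocol sections governs, and the protocol text places no limit on who at the sponsor may receive the data or on which fields they may see.

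**Conclusion.** Sections 8.4 and 9.1.17.1 conflict on when the sponsor may receive concentrations, and the only named safeguard is worded around laboratory staff rather than the recipient. That much rests on the text alone.

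The risk to the blind is conditional. If an early transfer carried draw and dosing times or another linking field, renumbering would not stop the sponsor from separating active from placebo among sampled subjects. Almost all draw times would be unique under the assumptions in step 3. Dose would be inferred correctly in roughly 71-88% of linked active subjects for an assumed CV of 70% down to 30%. If the manual withholds the linking fields, that risk goes and the inconsistency remains. This is worth correcting because the correction is cheap and protects decisions made on blinded data. It is not evidence against the prespecified primary analysis.

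**What to change.** Delete the sentence in 8.4 that allows disclosure to the sponsor before unblinding, so that both sections say after unblinding. The cost is that the population PK work starts later.

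If early release is needed, state the exception in 9.1.17.1 as well as 8.4. Limit recipients to a named group outside the study team. Say in the protocol, not only in the manual, that draw times, dosing times and any other linking fields are withheld from the study team until unblinding, and word the safeguard so that it covers the sponsor as recipient. This costs a few lines of text and a separate data flow for the PK group.

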8.5 Unblinding Procedure

The study drug blind shall not be broken by the investigator unless information concerning the study drug is necessary for the medical treatment of the subject.

For unblinding, the investigator may contact the emergency key code administration center and obtain allocation information of the study medication.

The date, time, and reason the blind is broken must be recorded in the document called Record of Early Blind-Breaking, and the same information (except the time) must be recorded on the eCRF.

If any site personnel are unblinded, study drug must be stopped immediately and the subject must be withdrawn from the study.

For details of unblinding procedure, refer to the manual for Breaking of Emergency Key Code.

8.6 Accountability and Destruction of Sponsor-Supplied Drugs

The site designee will receive the procedures for handling, storage, and management of study drug created by the sponsor, according to which the site designee will appropriately manage the sponsor-supplied drug. The investigator will also receive those procedures from the sponsor. The procedures include those for ensuring appropriate receipt, handling, storage, management, dispensation of the sponsor-supplied drug, and collection of unused medications from the subject as well as return of them to the sponsor or destruction of them.

The site designee will immediately return unused medications to the sponsor after the study is closed at the site.

9.0 STUDY PLAN

9.1 Study Procedures

The following sections describe the study procedures and data to be collected. For each procedure, subjects are to be assessed by the same investigator whenever possible. The Schedule of Study Procedures is located in [Appendix A](#).

9.1.1 Informed Consent Procedure

The requirements of the informed consent are described in Section [15.2](#).

Informed consent must be obtained prior to the subject entering into the study, and before any protocol-directed procedures are performed.

A unique subject identification number (subject number) will be assigned to each subject at the time that informed consent is explained; this subject number will be used throughout the study.

9.1.1.1 *Pharmacogenomic Informed Consent Procedure*

A separate informed consent form pertaining to pharmacogenomic research must be obtained prior to collecting a sample for Pharmacogenomic Research for this study (see Section [9.1.16](#)). The provision of consent to research in pharmacogenomics is independent of consent to the other aspects of the study.

9.1.2 Demographics, Medical History, and Medication History Procedure

Demographic information to be obtained will include date of birth, sex, alcohol use, and smoking status of the subject at Screening.

Medical history to be obtained will include determining whether the subject has any mental disorders other than MDD (including dysthymic disorder, generalized anxiety disorder, obsessive-compulsive disorder, as defined by DSM-IV-TR) that resolved within 1 year prior to signing of informed consent. Medical history of MDD (past major depressive episode) to be obtained will include determining whether the subject had MDD according to Section [9.1.4.2](#).

Medication history information to be obtained includes any medication that stopped prior to signing of informed consent and used for treatment of the current major depressive episode or accompanying symptoms. Name of medication used, dose level, unit, dose frequency, route of administration, and the dates of the initial dose and the last dose must be recorded.

9.1.3 Diagnosis of MDD

Diagnosis of MDD and other psychiatric disorders must be based on DSM-IV-TR criteria. In addition, the Mini International Neuropsychiatric Interview (MINI) must be used as an auxiliary diagnostic tool. MINI is a structured diagnostic interview designed to provide a brief standardized evaluation of major Axis I psychiatric disorders in DSM-IV-TR. The investigator can use the MINI after a training session for diagnosis of MDD. Only the version provided by the sponsor that has been validated in Japanese will be used in this study.

9.1.4 Assessments of Major Depressive Episode

9.1.4.1 Current Major Depressive Episode

The following items will be assessed for the current major depressive episode.

- Start date
- Symptom (Select from 9 symptoms listed below as defined by DSM-IV-TR.)
- Psychotherapy (yes or no)

<Symptoms of Major Depressive Episode>

- (1) Depressed mood most of the day, nearly every day, as indicated by either subjective report (e.g., feels sad or empty) or observation made by others (e.g., appears tearful).
- (2) Markedly diminished interest or pleasure in all, or almost all, activities most of the day, nearly every day (as indicated by either subjective account or observation made by others).
- (3) Significant weight loss when not dieting or weight gain (e.g., a change of more than 5% of weight in a month), or decrease or increase in appetite nearly every day.
- (4) Insomnia or hypersomnia nearly every day.
- (5) Psychomotor agitation or retardation nearly every day (observable by others, not merely subjective feelings of restlessness or being slowed down).
- (6) Fatigue or loss of energy nearly every day.
- (7) Feelings of worthlessness or excessive or inappropriate guilt (which may be delusional) nearly every day (not merely self-reproach or guilt about being sick).
- (8) Diminished ability to think or concentrate, or indecisiveness, nearly every day (either by subjective account or as observed by others).
- (9) Recurrent thoughts of death (not just fear of dying), recurrent suicidal ideation without a specific plan, or a suicide attempt or a specific plan for committing suicide.

9.1.4.2 Past Major Depressive Episode

The following items will be assessed for past major depressive episode.

- Start date and duration of each past major depressive episode.
- Antidepressant drug treatment for each past major depressive episode (yes or no). If the subject has received an antidepressant drug, category of the drug (select from SSRIs, SNRIs, or other antidepressant drugs.) and duration will be recorded.

